6.5 Standards and Safety of Participants

- All devices used in the study are FDA approved (DXA, RMR hood machine, NIRS, ActiGraph, ActivPAL, etc.).
- This study involves DXA scans –Female participants of child-bearing age are required to complete a pregnancy test before DXA scan.
- A nurse will perform any blood draws and all study staff assigned to perform lab procedures or RQ will be specifically trained to work with that equipment. This is training that is above and beyond the regular research CMH or standard research education.
- Appetite assessments: Blood will be collected via an IV catheter over 8 time points) over a period of 3 hours. Approximately 36mL (two samples at time 0, one sample at all other time points, 9 samples x 4 mL= 36 mL= 1.22 oz) of blood will be collected.
- Euglycemic clamp: Three baseline blood samples will be collected at the onset of the session to determine baseline glucose and insulin levels. The total amount of blood collected at baseline will be approximately 9 mL (3 samples x 3 mL/sample= 9 mL). Blood will be sampled every five minutes during the clamp procedure to monitor glucose levels. The total amount of blood collected to monitor glucose will be approximately 36 mL (36 samples x 1 mL/sample = 36 mL). Every 15 min we will also collect blood samples to store for assessment of insulin at study completion. The total amount of blood to assess insulin will be approximately 24 mL (12 samples x 2 mL/sample= 24 mL). During recovery, blood glucose is assessed every 10 minutes and insulin once. The total amount of blood collected during recovery is 8 mL (6 glucose samples x 1 mL= 6 mL; 1 insulin sample x 2 mL= 2 mL).
- Total amount of blood collected during the entire clamp procedure is approximately 77 mL (9 mL + 36 mL + 24 mL + 8 mL) or 15.6 teaspoons/2.6 ounces.

- The amount of blood is within the allowable amounts to be collected for research purposes.
- No subjects will be less than 16.5 kg

7.0 Data and Specimen Banking

- 7.1 Samples will be stored in the CCHLN biochemistry lab
- 7.2 Study ID, birth year, visit date only
- 7.3 CM research only, for the purposes of this study only
- 7.4 N/A – samples not retained for long-term research.

8.0 Genetic Analysis Information

N/A – no genetic analysis

9.0 Sharing of Results with Subjects

- 9.1 At the conclusion of the study, a report with the participant's study results will be shared with each participant. Results will include:

- Height and weight
- Blood pressure values
- Fitness percentile
- Resting metabolic rate
- Activity monitor data such as steps per day
- Two body composition scans with bone mineral density
- Grip strength

10.0 Study Timelines

10.1 Describe:

- Individual participation in the study will last approximately 35 days, but this time period can be extended to accommodate participant's schedules.
- Recruitment and data collection will last approximately 18 months.

11.0 Inclusion and Exclusion Criteria

11.1

Inclusion Criteria

- Males (~50%) and females (~50%)
- Age 14-17 (Tanner Stage III-V, as determined via self-assessment)
- Non-smoking
- Not currently involved in any other research study

- Willing to give informed consent to participate

Exclusion Criteria

- Age <14 or >18 at time of enrollment
- Restrained eater (>13 on the restraint section of the three-factor eating questionnaire; Current/past diagnosis of an eating disorder).
- Self-reported medical conditions (including, but not limited to, diabetes, Crohn's disease, etc.) that may affect adherence to the protocol, exercising safely, or alter metabolism
- Taking medications known to affect metabolism (e.g. thyroid medication, β -blockers, or stimulants).
- Gave birth in the past 12 months or <6 months post-lactation.

Individuals who are not yet adults (infants, children, teenagers) will be included in this study (teenagers age 14-17).

12.0 Vulnerable Populations

SHORT TITLE:

- Children/Minors (under 7 years of age)
- Children/Minors (7-17 years of age)
- Neonates (infants less than 30 days old)
- Neonates of Uncertain Viability (infants less than 30 days old)
- Non-Viable Neonates (infants less than 30 days old)
- Wards of the State
- Fetuses
- Pregnant Women
- Adults with impaired decision-making capacity
- CM Employees
- CM Students/Residents/ Fellows
- Economically or Educationally Disadvantaged Persons
- Prisoners

- This study involves children who are not yet adults. The study will be explained to them at the study visit as well as during the informed consent discussion.
- The research involves no more than minimal risk to the subjects.
- [HRP-416 - CHECKLIST - Children](#) has been reviewed.

Local Number of Subjects

- 12.1 This study involves four cohorts: normal weight/inactive, normal weight/active, OW,OB/inactive, and OW,OB/active. The goal is to accrue 10 participants in each cohort for a total of 40 study participants. We anticipate the need to enroll about 60 total participants to account for screen fails and dropouts.
- 12.2 We expect to make send our study letter to 2,000 potential participants, screen about 900, and enroll around 60, to get our final enrollment goal of 40. This is based off our previous AAAA submission with similar inclusion/exclusion criteria.
- 12.3 N/A – no chart review beyond what is required for screening.

13.0 Screening and Recruitment Methods

- 13.1 Participants will be recruited from previous Energy Balance research studies, from a recruitment list generated by CMH MIT, and a recruitment list generated from KUMC pioneers/frontiers. Recruitment letters and flyers will be mailed to the parents of potential participants from the above recruitment methods.

SHORT TITLE:

Additional recruitment methods include social media resources, the CCHLN website, dissemination of the study flyer to partner departments and institutions, and articles posted on the Scope using Daily E-News at Children's Mercy.

- 13.2 Participants will be recruited from CMH, KUMC, and the community.
- 13.3 When available, study staff will use previous contact with Energy Balance research participants (or potential participants that stated they were interested in other opportunities), CMH MIT generated data or KUMC generated data to pre-screen (or identify) potential participants. When not available, study staff will use a Redcap screener to verify eligibility.
- 13.4 Study staff will record, and request (from resources such as CMH MIT) only the minimum necessary identifiable data for the purposes of contacting participants prior to ICF and pre-screening. We are requesting a Waiver of HIPAA Authorization for recruitment and screening purposes only. Minimum necessary PHI on non-participants will only be kept until completion of enrollment.
- 13.5 We may disseminate the study flyer to other departments for the purposes of recruitment (Teen clinic, weight management clinic, etc).
- 13.6 Individuals will be contacted a maximum of 3 times (including voicemails), when following up after mailing a study letter.

14.0 Reimbursement, Payment and Tangible Property provided to subjects

- 14.1 Participants will be paid via pre-paid debit card. Participants will be paid when activity monitors are returned at the DXA/CRF visit \$175, and another \$125 at the insulin sensitivity visit.
- 14.2 Participants will be paid \$5 for each visit they attend as a travel reimbursement, with a max possible travel compensation of \$15 to be paid at the completion of the study.

Payments will be administered as follows:

Measurement Session #2: \$175 for study procedures

Insulin Sensitivity Visit: \$125 for study procedures, maximum of \$15 (\$5 per visit) for travel reimbursement

Total Compensation: \$300 for study procedures plus a maximum of \$15 for travel reimbursement totaling a maximum compensation of \$315.

- 14.3 N/A – no tangible property given

15.0 Withdrawal of Subjects

- 15.1 Non-compliance with the protocol.*
- 15.2 The study team will attempt to contact the participant for the purposes of determining a reason for withdrawal, attempting to reschedule, etc.*
- 15.3 If a participant decides to withdraw, all data up to the point of their withdrawal will be kept.*

16.0 Risks to Subjects

- 16.1*
 - Drawing blood from the participant's arm and hand include discomfort and/or bruising. There is a very low risk of infection, bleeding, clotting, or fainting.
 - Wearing activity monitors poses no known risks. However, the participant may feel some discomfort while initially getting used to wearing the monitors. In addition, a small percent of participants have developed a rash associated with the adhesive from the leg activity monitor. If any participant experiences any irritation, itching or redness while wearing either monitor, they will be instructed to stop wearing the monitor immediately and inform the study staff.
 - While the radiation used for the body scan (DXA scan) has no observable radiological or biological effect, there is always a risk associated with radiation exposure.
 - During the fitness test the participant will experience an increase in heart rate and blood pressure. Additionally, sweating will occur, and they may become fatigued, all of which are to be expected with exercise. It is also possible that abnormal responses may occur such as dizziness, unusually high increases in heart rate and blood pressure, and in rare instances, fainting. Trained personnel will be on hand during the fitness test. Emergency equipment is kept in the exercise testing room and all staff have been trained in its use. Following the fitness test, they may experience muscle soreness for a few days.
 - During the study the participant will be asked to eat three meals (breakfast and lunch during the appetite assessment, lunch following the clamp procedure). The study team will inquire about any food allergies the participant may have.
 - During and immediately after the clamp procedure there is a risk of hyperglycemia. We will monitor blood glucose every five minutes during the technique and for 1 hour following the technique.
 - There is also a slight risk of loss of confidentiality, meaning that someone could know the child participated in this study if they study team's

SHORT TITLE:

research records are hacked. The participant's confidentiality will be protected to the greatest extent possible.

- Possible physical discomfort from the pressure from the NIRS muscle cuff

16.2 Overall, the risks involved in this study are minimal. At this time we do not see any unforeseeable risks, but as information comes available we plan to report it to participants.

16.3 We will screen for pregnancy prior to completing DXA scans on women of child bearing age (all women enrolling in the study), but there are risks associated with radiation exposure.

16.4 Loss of confidentiality could affect parents/family of participants as well as participants.

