Insulin Sensitivity Visit: 5 hours. This study visit will take place at University of Kansas Medical Center Clinical and Translational Science Unit (KUMC CTSU) located on the Fairway campus. This visit will involve baseline blood samples and blood samples taken throughout the insulin sensitivity test.

- **Hyperinsulinemic euglycemic clamp.**

- The hyperinsulinemic-euglycemic clamp is the gold standard for assessing insulin sensitivity as stated by the World Health Organization. It allows the insulin levels to be 'clamped' at a constant state so that insulin stimulated by physiological measures can be assessed. Insulin sensitivity can be determined by the amount of glucose that is infused to maintain euglycemia. The higher the amount of glucose that needs to be infused while insulin is clamped, the more insulin sensitive the subject is.
- The hyperinsulinemic euglycemic clamp will be performed at the University of Kansas Medical Center Clinical and Translational Science Unit (KUMC CTSU), located at [name]. The CTSU contains 17 clinic rooms, 2 cognitive testing rooms, and open workspaces for up to 5 visiting study coordinators. The CTSU's infusion center has 11 infusion bays supported by two nursing stations and activity in the center has steadily grown. The center also supports research infusions and intensive and complex metabolic research assessments such as hyperinsulinemic-euglycemic clamps (see Morris et al. 2016). There is a CTSU medical monitor available for Adverse Events. The CTSU medical monitor is contacted when there is an urgent, medical concern / AE with the participant; The medical monitors are MD's or NP's / APRN's (aka Advanced Practice Registered Nurse). NOTE: This is in addition to the study-specific DSMB.

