- Participants will arrive fasted (12-hours overnight), and one catheter will be inserted into an antecubital vein of one arm to infuse insulin and 20% dextrose, and another catheter will be inserted into a contralateral vein in the hand/arm for blood sampling. The participant will rest quietly and we will collect 3 baseline blood samples to establish baseline glucose levels. If baseline values are <60 mg/dL the procedure will not continue. Once baseline assessments have been completed, a primed continuous infusion of regular human insulin plus albumin will be administered at a rate of $40 \text{ mU} \cdot \text{m}^2 \text{ body surface area}^{-1} \cdot \text{min}^{-1}$ along with a variable infusion of 20% dextrose to

maintain euglycemia to match baseline levels (expected 90-100 mg/dL). Blood glucose measurements will be completed every 5 minutes for determination of glucose infusion rate using a Nova Statstrip handheld glucometer and YSI analyzer as needed.

- After approximately 90 minutes of acclimatization, a 30-minute data collection period will occur. Insulin sensitivity will be determined as average glucose concentration and glucose infusion rate during this 30-minute period of euglycemia (defined as glucose concentration and glucose infusion rate coefficient of variation <10%).
- After this 30-min period, A 60-minute recovery period begins. Insulin infusion is stopped, and glucose infusion continues at the last rate for 30-min to prevent hypoglycemia. Glucose infusion is stopped 30 minutes into recovery if blood glucose levels remain at acceptable levels.
- Participants will be provided a full lunch meal (e.g., sandwich, potato chips, drink) following the cessation of insulin infusion to minimize the chances of hypoglycemia. Participants will be provided with a 20 mEq potassium pill to take with food. In rare instances hypokalemia can occur resulting from hyperinsulinemia and increased glucose disposal. Potassium supplementation helps prevent this from occurring.
- Following the cessation of glucose, all participants will remain under observation at the CTSU for the final 30 minutes of recovery to monitor for hypoglycemia.
- Participants can be released if participant is asymptomatic and blood glucose levels are acceptable at the end of the observation period.

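### Section 16 lists hyperglycemia as the clamp's only glucose risk and omits the hypoglycemia and hypokalemia that the clamp procedure itself guards against; secondarily, the protocol's only numeric glucose limit applies before insulin starts.

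*Combined protocol and SAP*

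**What the plan says.** The risk list in Section 16.1 has one entry on glucose during the clamp: "During and immediately after the clamp procedure there is a risk of hyperglycemia". It adds that glucose will be checked every five minutes during the clamp and for an hour afterwards. Section 16 contains neither hypoglycemia nor hypokalemia.

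The clamp procedure in Section 6.0 (Insulin Sensitivity Visit) reads differently. After insulin stops, "glucose infusion continues at the last rate for 30-min to prevent hypoglycemia". A full lunch is given "following the cessation of insulin infusion to minimize the chances of hypoglycemia". Then "all participants will remain under observation at the CTSU for the final 30 minutes of recovery to monitor for hypoglycemia". On potassium it says "In rare instances hypokalemia can occur resulting from hyperinsulinemia and increased glucose disposal", and each participant receives a 20 mEq potassium pill.

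On limits, Section 6.0 sets one glucose value, and it applies before insulin: "If baseline values are <60 mg/dL the procedure will not continue". Once insulin is running, dextrose is varied to "maintain euglycemia to match baseline levels (expected 90-100 mg/dL"). Section 20.1 has the nurses stop the clamp if problems arise, without defining a problem by a glucose value. Section 6.0 also provides: "The CTSU medical monitor is contacted when there is an urgent, medical concern / AE with the participant".

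**The concern.** Insulin is infused into 14- to 17-year-olds who are told to expect no benefit (Section 17.0). The risk section is where an ethics board or a new staff member looks for the clamp's hazards. As written, it names the glucose hazard in one direction only, and it is not the direction the procedure is built to prevent. If the permission/assent form repeats the sentence, families receive the same incomplete statement; the form is not available here.

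The second matter is smaller. The plan refuses to start a clamp below 60 mg/dL but does not say what to do if the same reading occurs during the infusion, beyond adjusting dextrose towards the target. Because the target is the participant's own baseline, and 90-100 mg/dL is only expected, someone who starts just above 60 could be held near that level.

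**Working it through.** **Risk text against procedure text.** No arithmetic applies to the main point.

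| Hazard | Section 16 (risks) | Section 6.0 (clamp procedure) |
|---|---|---|
| Hyperglycemia | Named as the glucose risk | No step expressly against it |
| Hypoglycemia | Not mentioned | Three steps: continued dextrose, meal, observation |
| Hypokalemia | Not mentioned | Named as rare; potassium given |

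Hyperglycemia may be a slip for hypoglycemia, or a deliberate reference to the dextrose infusion. On either reading, two hazards that the procedure acts on are missing from the list.

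**Numeric glucose values by stage.**

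- Before insulin: do not continue below 60 mg/dL.
- During insulin: a titration target (baseline) and a steady-state definition (coefficient of variation, CV, below 10%). Neither is a stop or rescue limit.
- Three decisions after insulin starts: stopping the clamp (Section 20.1), stopping dextrose in recovery, and release (both Section 6.0). None of the three has a glucose value; the last two depend on levels being acceptable.

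**How often a 60 mg/dL limit would be crossed in the 30-minute window.** The documents give no baseline distribution, so these inputs are assumed:

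- Baseline glucose is Normal with mean 95 (middle of the expected 90-100) or 90 (its lower end), and SD 5, 8 or 10.
- Readings vary normally around target T with CV 5% or 10%; 10% is the plan's ceiling for this window.
- Five-minute readings over 30 minutes give 30/5 + 1 = 7 readings, treated as independent. This overstates the result if they are positively correlated.
- N = 40 completers (4 cohorts x 10, Section 12.1).

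Formulas:

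- Starting at 60-75 mg/dL: 40 x [Phi((75 - mean)/SD) - Phi((60 - mean)/SD)]. For mean 90, SD 10: 40 x (0.0668 - 0.0013) = 2.6.
- At least one of 7 readings below 60: 40 x integral over T from 60 upwards of f(T) x [1 - (1 - Phi((60 - T)/(CV x T)))^7] dT, where f is the baseline density.

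| Mean | SD | Start at 60-75, of 40 | Any reading <60, CV 5% | Any reading <60, CV 10% |
|---|---|---|---|---|
| 95 | 5 | 0.001 | 0.00 | 0.08 |
| 95 | 8 | 0.25 | 0.005 | 0.27 |
| 95 | 10 | 0.90 | 0.05 | 0.59 |
| 90 | 5 | 0.05 | 0.00 | 0.29 |
| 90 | 8 | 1.2 | 0.04 | 0.84 |
| 90 | 10 | 2.6 | 0.20 | 1.51 |

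**Risk by individual target.**

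- T = 61, CV 5%: (60 - 61)/(0.05 x 61) = -0.33, so about 37% of single readings fall below 60. The chance of at least one in 7 is 1 - 0.63^7, about 96%.
- T = 75, CV 10%: (60 - 75)/7.5 = -2, so 2.3% per reading and 1 - 0.977^7, about 15%, over 7.
- T = 95, CV 10%: -35/9.5 = -3.7, so under 0.1% over 7.

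The risk to any one participant is therefore greatest just above 60. With CV 5%, nearly all the expected count comes from targets below 70. With CV 10% it also draws on higher targets, because few participants start so low.

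**What this leaves out.** The roughly 90 minutes before the window have no stated limit on variation and are not covered. No total reading count is used, because Section 6.0 describes 90 + 30 = 120 minutes of insulin, while the sampling in Section 6.5 (36 x 5 and 12 x 15) spans 180.

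**The case against.** The strongest reply is that the hazard is disclosed and managed in the same protocol. Section 6.0 names hypoglycemia three times and acts on it each time, and it gives potassium for hypokalemia. On this view Section 16.1 contains a one-word slip, not a design gap. That is a fair description of the first part: it is an internal inconsistency, and correcting the text resolves it. It still needs correcting, because Section 16 is the protocol's risk statement.

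On the missing limit, the reply is stronger. Readings every five minutes drive dextrose back towards baseline, no clamp starts below 60, nurses can stop the procedure, and a medical monitor is on call. That monitor is contacted for an adverse event as well as an urgent concern, so escalation is not confined to emergencies. The CTSU already runs clamps, and its operating procedures may contain numeric action limits. The gap is therefore established for this protocol only, and it ranks second. What stands is that the sponsor thought a number necessary before insulin starts, while the protocol gives none afterwards.

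A stop at 60 also fits awkwardly with a target just above 60: such a clamp would probably be started and then trigger the rule. That is a real cost.

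Two stronger readings are tempting. One is that the minimal-risk rating in Section 18.0 rested on this bullet. Nothing shows that: the IRB makes the final determination, and the protocol it belongs to includes the clamp procedure. The other is that the DSMB comparison of adverse event rates with pre-study assumptions (Section 20.1) uses this list. Section 16 gives no numeric event rates, and no section says that it supplies those assumptions.

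**Conclusion.** The main point holds on the text alone. Section 16 names the clamp's glucose risk as hyperglycemia only and leaves out hypoglycemia and hypokalemia, both of which Section 6.0 acts against. It applies to every clamp and should be corrected.

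The secondary point holds for this protocol: the only numeric glucose limit precedes insulin. It concerns a rare event. On the assumed distributions, 0 to 0.6 of 40 participants would have any window reading below 60 (0 to 1.5 if the baseline mean is 90). The upper figures need SD 10 and CV at the 10% ceiling, and the earlier phase is not covered. A reader might infer that participants are unprotected from low glucose during the infusion; the safeguards in Sections 6.0 and 20.1 do not support that. Whether CTSU procedures or the permission/assent form already deal with either matter cannot be judged from these documents.

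**What to change.** 1. Section 16.1: state hypoglycemia as the clamp's glucose risk, keeping hyperglycemia as a second risk if it was intended. Add rare hypokalemia. Check the permission/assent form for the same sentence and correct it if present.
2. Sections 6.0 and 20.1: if CTSU procedures already set an in-infusion limit, cite it. If not, carry the plan's own 60 mg/dL limit into the infusion. On a reading below 60, raise dextrose at once and repeat on the YSI analyzer already listed. If confirmed, stop insulin, continue dextrose and call the CTSU medical monitor.

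The values for stopping dextrose and for release remain the sponsor's clinical choice, and no floor on the target is proposed.

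Both edits fit in one amendment, with no extra visit and no change to the clamp target or to how insulin sensitivity is obtained. The cost is that a rare clamp stops early and its value is lost to the hypothesis 2 analysis: about 0 to 2 of 40 from the 30-minute window (1.51 rounded up), possibly more from the earlier phase. The participants most exposed are those whose target is only just above 60. The window figure counts any reading below 60, so the confirmation step should bring actual stops below it and limit stops caused by handheld meter error.
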